# Application steps in the intervention group

The literature has been examined in determining the duration of respiratory exercise to be applied to elderly individuals in the study group. Taking into consideration the methods and suggestions of all these studies, respiratory exercises are planned in this study. Breathing exercises; Between 18.02.2019 -09.05.2019, for 12 weeks, three days a week (Monday, Tuesday, Thursday) in groups of 5-6 people (2 groups of 6 people, 4 groups of 5 people in total, 10.00-15.30 hours) between each group at the same time of the day, 30 min. will be applied for a while. During the breathing exercise, no special clothing or supplies will be needed. Disruptions in participating in the exercise program will be compensated for at the specified time and day in partnership with the elderly individual and the researcher. The wind rose to be used during the exercise will be provided by the researcher. All types of breathing exercises will be taught to older individuals on the first day of application and will be shown again by the researcher prior to the application throughout the application. Dizziness that may occur during breathing exercise may occur. Elderly individuals will be reminded of this before each application, and if they experience dizziness, they will be asked to wait for the dizziness to pass by pausing the exercise for a short time. The application of the breathing exercise program is as follows;

- I. Pursed Lip Breathing Exercise (using the Wind rose)
- The individual is seated in a position where he feels comfortable and with clothes,
- First, breathe slowly through the nose,
- Lips contract like a whistle
- The wind rose is kept at the level of the mouth at a distance of 25 cm,

• The breath is discharged slowly and for a longer period of time (at least twice the breathing) by blowing from the shrunken lips to the wind rose,

- Power should be used to exhale,
- This process continues until the breath is interrupted,
- A break is taken for 30 seconds, then the procedure is repeated (Total 10 minutes)
- 2 minutes break.
- II. Diaphragmatic breathing exercise
- The active hand is placed on the stomach and the other hand on the chest,
- Breathing slowly through your nose,
- The abdomen is filled with air and the hand rises,
- The rib cage should rise less than the abdomen,
- Then, breathing slowly through the mouth,

- 30 seconds break and the process is completed (10 minutes in total),
- 2 minutes break.
- III. Cough exercise
- Then a deep breath is taken through the nose,
- After the chest is fully enlarged, mouth is exhaled,
- This process is repeated twice,
- Take a deep breath for the third time and hold it for 2 seconds,
- Then, two times, "huh huh" sound is made and the mouth is exhaled,
- 30 seconds break,
- Then this process is repeated (Total 10 minutes).

# Application steps in the control group

No breathing exercise will apply to elderly in the control group. Individuals will continue their daily lives.

### Post-test

One day after the end of breathing exercise application, between the dates 10.05.2019 - 14.05.2019, elderly individuals will be called by calling from the room telephones in the physical therapy unit. will be re-evaluated in individuals in both groups

Official Title of the study: Effect of breathing exercise on some physiological parameters, sleep quality and vitality in elderly.

NCT number: not yet have

Date of the document: January 1, 2019

Study population and sample

The population of the study consists of 294 individuals living in the 75th Year Nursing Home Elderly Care and Rehabilitation Center affiliated to Ankara Provincial Directorate of Family and Social Policies. In the sample calculation of the study, taking into account the results of similar studies in the literature with the GPower 3.1.9.4 program, it was calculated that it would be sufficient to take a total of 52 individuals, with a margin of error of 0.05, 80% test power, 26 elderly individuals per group. Considering that such studies may be lost in the process, 20% of the minimum sample number (11 individuals) was added to the study in order not to decrease the statistical power of the research. A total of 32 elderly individuals in the intervention group and 31 elderly individuals in the control group were planned.

Stratified randomization method will be used in the research. Elderly individuals who meet the inclusion criteria will be separated into layers by considering the age (65-74 years -75 years and older) and gender (women-men) after the pre-test data are obtained, and then by simple randomization method using SPSS program in computer environment. will be assigned to the intervention and control groups.

Data collection tools

Research data will be obtained by using the data collection tools mentioned below.

- Introductory Information Form
- Pittsburg Sleep Quality Index (PSQI)
- Subjective Vitality Scale (SVS)
- Physiological Parameters Evaluation Form

Introductory information form

The form was created by the researcher by examining the related literature. In this form, there are 9 closed-ended questions that question the socio-demographic characteristics, health conditions and habits of the elderly.

Pittsburg sleep quality index (PSQI)

Pittsburg Sleep Quality Index (PSQI) was developed by Buyse et al. In 1989 and its adaptation to Turkish, validity and reliability study was done by A arg n et al. The scale that determines the quality of sleep consists of 18 self-report questions and evaluates the quality of sleep in the last 4 weeks. PSQI has 7 components such as subjective sleep quality, sleep latency, sleep duration, habitual sleep effectiveness, sleep disturbance, use of sleep medication, daytime dysfunction and each component is evaluated between 0 and 3 points. The total score ranges from 0-21. The total score higher than 5 indicates that the sleep quality is bad. The sensitivity of the scale was 89.6%, and its selectivity was 86.5%. Cronbach internal consistency coefficient of the scale is 0.80 in the Turkish validity and reliability study and later studies.

Subjective vitality scale (SVS)

Subjective Vitality Scale (SVS) The scale was developed by Ryan and Frederick in 1997, and its validity and reliability study was performed by Uysal et al. (2014). Z is a 7-point Likert (1 absolutely disagree-7 strongly agree) measurement tool based on self-report, consisting of 7 items. By collecting the points of all items in the scale, the total subjective fitness score of the individual can be obtained. The second item of the scale is reversed. The scale in the scale ranges from 7 to 49. High scores obtained from the scale indicate that the individual's subjective fitness level is high. Cronbach internal consistency coefficient of the scale is 0.87. The test-retest correlation coefficient was found to be 0.79. In the explanatory factor analysis applied for the construct validity of the scale, it was determined that the items were collected in one factor and the single factor model explained 62% of the total variance. Confirmation factor analysis result fit index values 2 = 19.95, sd = 8; RMSEA = 0.08, AGFI = 0.93, GFI = 0.97, NFI = 0.98.

Physiological parameters evaluation form

As physiological parameters;

• It is a form prepared by the researcher to evaluate lung functions. In this form; forced vital capacity (FVC), air volume removed in the 1st.second of forced expiration (FEV1), FEV1 / FVC ratio and percentages

• In the form created to evaluate cardiological functions; heart rate, blood pressure, heart rate, oxygen saturation are forms to evaluate and record.

Cardiac functions will be evaluated using a manual sphygmomanometer and a pulse oximeter, while pulmonary functions will be assessed by a physiotherapist using a spirometer.

Dependent variables

Respiratory function test results, systolic / diastolic pressure, heart rate and oxygen saturation, the score obtained in the Pittsburg Sleep Quality Index, and the Subjective Vitality Scale are dependent variables of the study.

Independent variable

The breathing exercise program is the independent variable of the study.

Evaluation of the data

The data will be evaluated using SPSS (Statistical Package for Social Sciences) 16.0 package program. For descriptive statistics, frequency, percentage values, average and standard deviation will be used. Chi-square test will be used for categorical comparisons. In the statistical evaluation of quantitative variables, the compatibility of the data with the normal distribution will be examined with the Kolmogorov Smirnov test. If the data are suitable for normal distribution, whether the Pittsburg Sleep Quality Index score, Subjective Fitness Scale score, pulmonary function test results, systolic / diastolic pressure, heart rate and oxygen saturation values change between the intervention and control groups before and after respiratory exercise, the significance of the difference between the two partners is important. Intra-group change will be evaluated by t-test in dependent groups and two-way analysis of variance in repeated measurements of groups. The level of significance will be taken as p < 0.05. The effect size will be determined by Cohen's d value. In general, if the d value is less than 0.2, it is defined as a weak effect, medium if 0.5, and strong if it is greater than 0.8. In the evaluation of bidirectional variance analysis, partial eta square (p 2) will be used as the effect value. Generally, if the value of p 2 is less than 0,01, the effect size is weak, it is defined as medium if it is 0,060, and strong if it is greater than 0,140.

In order to prevent bias in the evaluation of the data, the data recorded in the database will be analyzed by a statistical expert independent of the researcher. The data will be sent to the statistical specialist by coding as "Group 1" and "Group 2", without specifying the name of the intervention and control groups.

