# **Pre-test**

The pre-test application is planned to be done between 29.01.2019 -03.02.2019. In the physical therapy unit of the nursing home, a suitable area will be determined by the researcher and specialist physiotherapist, and measurement devices will be placed, elderly individuals in both groups will be called from the room phone and called for measurement. In order to prevent the data from being affected by the measurements, introductory information data sheet, Pittsburg Sleep Quality Index, Subjective Vitality Scale will be applied, individuals will be rested during this period, and then cardiological parameters will be evaluated, and finally lung functions will be evaluated.

A manual sphygmomanometer and a pulse oximeter device will be used to assess heart function. Sphygmomanometer is of Perfect Aneroid type. The manometer chamber and the spoon spoon are nickel plated chrome. The manometer is 48 mm in diameter, the cuff outer cloth dimensions are 13x47 cm (+/- 2 cm), the cuff outer cloth is hooked, the cuff inner tube hoses are made of double-layer, vulcanized rubber. It is suitable for adult use. Finger pulse oximetry device has arterial oxygen saturation and pulse measurement feature. It provides a graphical view of the pulse. It is suitable for all ages. Evaluation steps are as follows;

• The individual is informed before evaluating his heart functions.

• The individual is placed in a position where the individual can be comfortable from the measurement. He should not have used tea, coffee and cigarettes until 15 minutes before the measurement.

- The individual is rested for 3-5 minutes
- Heart rate is measured from the radial artery for one minute

• For the systolic / diastolic blood pressure, the appropriate arm is selected, the clothes are relaxed / removed, the arm is positioned (must be at 45 heart level), the appropriate sleeve is selected (wrap the arm sufficiently). Next, the location of the brachial artery is determined, the air of the cuff is completely evacuated, the lower edge of the cuff is taken 2-2.5 cm above the place where the brachial artery is palpated, the middle point of the cuff is placed on the brachial artery. The receiver of the stethoscope is placed on the brachial artery without touching the sleeve and clothes and the earpiece is placed on the ear, the cuff is inflated to 30 mmHg above the previously determined systolic blood pressure value, then the cuff air is discharged to be 2-3 mmHg / second.

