• Blue, black, green, brown, red nail polish, if any, in the individual before the oxygen saturation measurement is deleted, artificial nail is removed,

- It is placed on the hand and / or toenail of the light source part of the pulse oximeter,
- Measurements are made for 30 seconds and then the device is removed from the finger
- The data are recorded on the data form created by the researcher.

Evaluation of lung functions will be done in the presence of a specialist physiotherapist. The specialist physiotherapist does not know the elderly individuals in the experimental and control groups. Spirometry will be used to evaluate lung function. Spirometry is the basic device of respiratory function test laboratories. It consists of the electronic part where the measurement is made and the mouthpiece that the patient breathe. Cosmed Pony FX - Desktop Spirometer and disposable mouthpieces suitable for the device will be used in the study. This type of spirometer enables testing without the need for a computer. It has an internal memory where patient information can be stored. It is used with two-way digital turbine flowmeter. Pulse function test measurement application steps are as follows;

- Elderly individuals are informed before spirometry is applied.
- The height of the elderly person, body weight is measured and recorded with his age
- Individual disposable mouthpiece is placed in the entry section of the tool.

• The individual puts the mouthpiece in his mouth with his lips, but not to bite with his teeth. It is important that the lips close well. Otherwise, leakage will occur. This causes incorrect measurement.

• The nose of the individual who is connected to the spirometer device with the help of a mouthpiece is closed with a special latch before the measurement.

- The individual breathes calmly first (4-5 times)
- It takes a hard, deep and fast breath after normal breathing.

• It is also fast, challenging and exhaled with the command to exhale. Breathing should take at least 6 seconds.

• This process must be repeated at least 3 times.

The test results are compared with the expected values (predicted values) pre-calculated in healthy individuals of the same age, height and gender by the software found in the spirometer

device and expressed as a percentage of these values. The obtained results will be sent to the researcher within 15 days in pdf format by the authorized firm of the spirometer device.

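### Allocation is called stratified but uses simple randomisation within strata, which as ordinarily understood adds no age or gender balance and does not fix the planned 32/31 split

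*SAP*

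**What the plan says.** The SAP, under Study population and sample, states: "Stratified randomization method will be used in the research". Eligible residents are divided by age (65–74, 75 and over) and gender, which makes four strata. They are then allocated; the timing and rule are given as "after the pre-test data are obtained, and then by simple randomization method using SPSS program in computer environment". Neither document gives an allocation ratio, a block size or a number per stratum.

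The same SAP section sets the arm sizes: "A total of 32 elderly individuals in the intervention group and 31 elderly individuals in the control group were planned". The protocol, under Application steps in the intervention group, builds its exercise timetable on "2 groups of 6 people, 4 groups of 5 people in total".

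For the analysis, the SAP (Evaluation of the data) says: "Intra-group change will be evaluated by t-test in dependent groups and two-way analysis of variance in repeated measurements of groups". No age or gender term is named.

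**The concern.** Stratifying is meant to make the arms alike on the chosen factors. It does so only when assignment within each stratum is restricted, by blocks or by a fixed count per arm. Simple randomisation within strata has no such restriction, so the plan names a protection that its stated rule does not deliver. The same rule leaves the arm sizes random, although the SAP plans 32 and 31 and the exercise timetable assumes 32.

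Part of the outcome set is protected anyway. Spirometry results are expressed relative to "healthy individuals of the same age, height and gender", and the SAP's lung function form records "FEV1 / FVC ratio and percentages". Repeated-measures comparisons also remove stable baseline differences. Neither protects against an effect of age or gender on the 12-week change in blood pressure, heart rate, oxygen saturation, PSQI, vitality or raw FVC and FEV1. If one arm happens to be older or to hold more women, the planned analysis has no term to account for it.

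**Working it through.** **Inputs from the documents.** Required sample 52 (26 per group), loss allowance 11, planned arms 32 and 31 (SAP, Study population and sample); exercise groups 2 of 6 and 4 of 5 (protocol, Application steps in the intervention group).

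**Assumptions.** Independent 1:1 assignment. Stratum sizes are not given, so a range is shown. The 20-point threshold is a choice made here for illustration.

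**1. The plan's own counts.** 20% of 52 = 10.4, rounded up to 11; 52 + 11 = 63 = 32 + 31. The exercise groups total 2×6 + 4×5 = 32. These agree with each other.

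**2. Equivalence to unstratified assignment.** With strata of n1 to n4 people, each person assigned independently with probability 1/2, any particular allocation list has probability (1/2)^(n1+n2+n3+n4) = (1/2)^63. That is also its probability when the strata are ignored. Simulation (200,000 runs) agrees. The SD of the between-arm difference in gender share was 0.128 with and without strata for sizes 16/16/16/15, and 0.126 with and without for 25/18/12/8.

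**3. Arm sizes.** The number in the exercise arm is X ~ Binomial(63, 1/2), whatever the stratum sizes.
- P(X = 32) = C(63,32)/2^63 = 0.099.
- P(X = 31 or 32) = 2 × 0.0993 = 0.199.
- Central 95% range for one arm: 24 to 39.

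**4. Imbalance on one factor.** If m of 63 have the factor, let A ~ Binomial(m, 1/2) be those with it in the exercise arm and B ~ Binomial(63−m, 1/2) those without. The difference in share is D = A/(A+B) − (m−A)/(63−A−B). Exact results:

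| m of 63 | P(\|D\| ≥ 0.20) |
|---|---|
| 13 | 0.054 |
| 19 | 0.091 |
| 25 | 0.112 |
| 32 | 0.130 |

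**5. Imbalance of 20 points or more on age or gender (either one).** By simulation, for three assumed layouts with the two factors about unrelated:

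| Stratum sizes | Probability |
|---|---|
| 3, 10, 10, 40 | 0.11 |
| 9, 10, 22, 22 | 0.21 |
| 16, 16, 15, 16 | 0.24 |

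**6. The same quantity under restricted allocation.** Give half of each stratum to each arm and place odd persons so that the totals are 32 and 31. In the worst case both strata of one gender (w people in all) are odd and both odd persons go to the arm of 32. The difference is then (w/2 + 1)/32 − (w/2 − 1)/31. This is largest at w = 2: 2/32 − 0/31 = 0.0625. Enumerating every possible set of four stratum sizes gives the same maximum, 6.25 points.

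**7. Power.** The SAP gives no effect size, so d is solved from 26 per group at 80% power and alpha 0.05.

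| Assumption | 32/31 | 38/25 |
|---|---|---|
| Two-sided, d = 0.79 | 87.2% | 85.7% |
| One-sided, d = 0.70 | 86.4% | 85.1% |

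These are before dropout. The loss from unequal arms is 1.3 to 1.5 points.

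**The case against.** The strongest reply is that the authors did not mean independent assignment. The sentence is loosely worded. Around it the plan names a stratified method, allocates after the pre-test so that the full list is available, and fixes 32/31 and a timetable for 32. A random draw of a fixed number from each stratum would fit all of this. That reading is plausible, and on it the design would balance. But neither document states it, and a person following the text could not reproduce it. The wording needs changing on either reading.

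The second reply is that little is lost. Simple randomisation is valid, there is no systematic bias, and the power cost is small; all of this stands. The documents also give no evidence that age or gender alters the 12-week change. As an assumed illustration, if a factor shifts the change by 0.5 SD, a 20-point imbalance moves the contrast by 0.5 × 0.20 = 0.10 SD, against a back-solved d of about 0.79. Even in the least favourable layout above, no 20-point imbalance occurs about three times in four. This limits the severity, but it does not justify keeping a rule that fails its own purpose when a better one is free.

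Third, 32/31 may be a recruitment target, and exercise groups of 5 or 6 could be rearranged for other counts. This is fair. The mismatch on arm size is an inconsistency in the plan rather than a serious practical obstacle.

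Finally, adjusting the analysis for age and gender would help on either reading, and leaving strata out of the analysis after restricted allocation tends to make tests conservative when the strata predict outcome. Adjustment would be a useful complement, but restricted allocation is sound without it.

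**Conclusion.** The concern holds. As written, the strata do no work: the stated rule is statistically identical to unstratified randomisation, and the planned 32/31 would arise about one time in five (one in ten with 32 specifically in the exercise arm). An imbalance of 20 points or more on age or gender has a probability of 11% to 24% over the assumed layouts, whereas restricted allocation caps the difference at 6.25 points.

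The conclusion rests on simple randomisation being taken as independent 1:1 assignment. The arm-size figures do not depend on stratum sizes; the imbalance probabilities do. The consequence is avoidable chance imbalance, with no bias and no material loss of power. The change should be made; confidence is medium because the authors may have intended a fixed draw per stratum.

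**What to change.** In the SAP, replace simple randomisation with restricted allocation within strata. Once all pre-tests are complete:

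1. Put the members of each age-by-gender stratum in computer-generated random order.
2. Assign half of each stratum to each arm.
3. Place the odd persons by a random rule written down beforehand that fixes the totals at 32 and 31, or within one of each other. With 63 people, one or three strata must be odd. With three, a separate coin toss for each could give 33/30, so the rule has to treat the odd persons together.

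As a minor alignment, the protocol's Pre-test section says "elderly individuals in both groups will be called from the room phone and called for measurement". No groups exist at that stage under the SAP, so this should refer to all eligible participants.

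The cost is wording only. The full list is known before allocation, and the same software session and the same participants are used.

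### The SAP makes its between-group comparison depend on an unspecified Kolmogorov-Smirnov check with no alternative branch, so it is unclear which analysis decides H01–H04 if the check fails.

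*SAP*

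**What the plan says.** The section of the SAP on evaluation of the data states that "the compatibility of the data with the normal distribution will be examined with the Kolmogorov Smirnov test". The sentence that lists sleep quality, vitality, lung function, blood pressure, heart rate and oxygen saturation then begins "If the data are suitable for normal distribution, whether the Pittsburg Sleep Quality Index score" and ends, in garbled translation, with whether these values "change between the intervention and control groups before and after respiratory exercise, the significance of the difference between the two partners is important". This appears to mean a test of the difference between two means.

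A separate sentence follows. It assigns within-group change to a paired t-test and names a two-way repeated-measures ANOVA. It does not repeat the normality condition. The section then adds "The level of significance will be taken as p < 0.05".

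Neither document gives a rank test, a transformation or any other route for data judged non-normal. Also unstated are the K-S version (with or without correction for an estimated mean and SD), its significance level, the data to be tested (by arm, by time point, pooled, change scores or residuals), and whether one failing sample is enough to close the gate.

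On the outcomes, the SAP describes the PSQI as a sum of seven components each scored 0 to 3: "The total score ranges from 0-21". The protocol's pre-test section says SpO2 is read from a finger pulse oximeter, without giving its display resolution.

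**The concern.** A conditional plan needs both branches, and this one has only the first. If an outcome fails the check, either the repeated-measures ANOVA still stands as the between-group test or nothing does, and the text does not settle which. The test would then be chosen after the data are seen, across about nine outcomes (FVC, FEV1, their ratio, systolic and diastolic pressure, heart rate, SpO2, PSQI, vitality).

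Adding a fallback would not cure the rule, because the gate measures the wrong thing. A t-test or ANOVA needs approximately normal residuals or means, and about 31 per arm generally supplies the latter. K-S applied to raw values also responds to rounding, which does little harm to a comparison of means. Its result depends heavily on a software choice the SAP leaves open.

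**Working it through.** **The plan's own figure.** The SAP states "with a margin of error of 0.05, 80% test power, 26 elderly individuals per group" but no effect size, so 52 cannot be reproduced from its inputs. Back-solving a two-sided t-test gives d = 0.79; d = 0.8 requires 25.5, rounded to 26 per group. The allowance does reproduce: "20% of the minimum sample number (11 individuals) was added", and 0.20 × 52 = 10.4, taken as 11; 52 + 11 = 63 = 32 + 31, as in "A total of 32 elderly individuals in the intervention group and 31 elderly individuals in the control group were planned". I therefore used about 31 per arm, and 26 per arm for the minimum.

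**Assumptions.** The documents give no mean, SD or shape for any outcome. Assumed: SpO2 in whole percent, SD 1.5 to 3; PSQI in whole points, either near-normal (mean 7, SD 3–4) or right-skewed (mean 5–6); pre-post correlation 0.6; two-sided 5% tests.

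**Why rounding matters.** K-S measures D, the largest gap between the sample's step function and a fitted normal curve. For a variable rounded to whole units, the tallest step is about 0.399/SD, so a gap of about half that exists even with no sampling error:
- SpO2, SD 1.5: 0.5 × 0.399/1.5 = 0.133
- SpO2, SD 2: 0.5 × 0.399/2 = 0.100
- Vitality, SD 8: 0.5 × 0.399/8 = 0.025

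At n = 31 the 5% critical value is about 0.156 with the Lilliefors correction (simulated from normal samples) and 1.358/√31 = 0.244 without it. Narrow SpO2 starts close to the first threshold and far from the second. Vitality is far from both.

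**Simulated failure rate, one sample of n = 31.**

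| Outcome (assumed) | Lilliefors | Uncorrected |
|---|---|---|
| SpO2, SD 1.5 | 76% | 5% |
| SpO2, SD 2 | about 50% | about 1% |
| PSQI, right-skewed | 57% | 4% |
| PSQI, near-normal | about 20% | under 1% |

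**At 26 per group (20,000 trials), Lilliefors.** Per sample, SpO2 fails 67% (SD 1.5), 40% (SD 2) and 20% (SD 3) of the time; near-normal PSQI 13–19%; skewed PSQI 48–63%; vitality and heart rate 6–7%. If any one of the four arm-by-time samples can close the gate, the SpO2 figures become 99%, 87% and 59%.

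**Is the ungated test valid?** At 26 per group, the t-test on post-test values or on change had type I error of 4.45% to 5.3% across all scenarios. At 32/31, the change-score t-test and ANCOVA held 4.5–5.1%. With two time points, the change-score t-test is the group-by-time test.

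**Power at a 0.5 SD effect, 32/31, correlation 0.6.** The standard error factor is √(1/32 + 1/31) = 0.252. For unrounded data:
- Change score: SD factor √(2 × (1 − 0.6)) = 0.894; noncentrality 0.5/(0.894 × 0.252) = 2.22; power about 59%.
- ANCOVA: SD factor √(1 − 0.6²) = 0.8; noncentrality 0.5/(0.8 × 0.252) = 2.48; power about 68%.

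Rounding SpO2 with SD 1.5 raises the variance to 2.25 + 1/12 = 2.333. The effect becomes 0.75/√2.333 = 0.491 SD and the correlation 0.6 × 2.25/2.333 = 0.579. The noncentralities fall to 2.12 and 2.39, giving power of about 55% and 65%. Simulation agrees:

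| Analysis | SpO2 | Skewed PSQI |
|---|---|---|
| Planned group-by-time (change) test | 54% | 57% |
| Rank test on change | 52% | 60% |

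ANCOVA gives 64–66% across the two outcomes.

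**The case against.** Four points can be made for the plan.

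1. **Scope.** A reader might infer that the gate controls every between-group analysis, so that a failing outcome has no planned test. The text does not establish this. The repeated-measures ANOVA, whose group-by-time term compares the arms, is in the next sentence without the condition. Extending the condition to it is plausible but not explicit. This narrows the point to an ambiguity over which analysis decides the hypotheses.

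2. **Likelihood.** A reader might infer that SpO2 and PSQI will probably fail. That does not follow. Under uncorrected K-S the failure rates above are 5% or less, and near-normal PSQI fails only about one time in five even with Lilliefors. Whole-number scoring alone is not enough, as vitality and heart rate show. Similar figures for blood pressure would require a rounding rule, such as readings to 5 mmHg, which the protocol does not state.

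3. **Power.** A reader might infer that falling back to a rank test would be costly. Against the planned change-score test, a rank test on change costs about 2 points for SpO2 and nothing for PSQI. A larger loss appears only if the comparator is ANCOVA, which is not in the SAP.

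4. **Safeguard.** The SAP sends the data, with arms coded, to an independent statistician. This limits choosing a test to favour an arm, but it does not say which test to run.

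What survives is the one-sided condition, the unspecified check, and a gate that responds to features that do not impair the analysis.

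**Conclusion.** The concern holds in limited form. The between-group comparison is conditional on a K-S check of unstated version and unstated data, there is no other branch, and the status of the repeated-measures ANOVA is unclear. Whether narrow or skewed outcomes pass may turn on the version used: a gap of about 50–76% against 1–5% for SpO2 with SD 1.5–2. These rates rest entirely on assumed distributions, rounding and sample definition; they show what can happen, not what is expected. That the gate is unnecessary rests on firmer ground, since type I error stayed near 5% in every scenario tried. This should be corrected, but it does not invalidate the trial.

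**What to change.** Delete the normality condition. For every dependent variable, whatever its distribution, analyse the post-test value by ANCOVA with arm, that variable's own pre-test value and the two stratification factors (age group and sex). Report the adjusted difference with its 95% confidence interval, and state that this analysis decides H01–H04. Name one fixed sensitivity analysis, for example a rank or bootstrap analysis, that does not replace the main result.

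Removing the condition from the planned t-test and ANOVA would be enough to cure the gate. ANCOVA is preferred because it uses data the trial already collects and, under the assumptions above, adds roughly 10 points of power. The cost is SAP wording only, and SPSS can fit the model. The one small downside is that the sensitivity analysis may need software other than SPSS 16.
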